| Chief Investigator | [name] Department of Anaesthesia University Hospital, Coventry, [name] Contact no: [name] [name] |
| Principle Investigator | [name] Department of Anaesthesia University Hospital, Coventry, [name] Email: [contact] |
| Co-investigators | [name], [name] Department of Anaesthesia University Hospital, Coventry, [name] Contact number [name] Email [contact] |
| Sponsor | University Hospitals Coventry & Warwickshire NHS Trust |

[figure not shown]
TRIAL SUMMARY

| | | |
|-----------------------------|---|--|
| Full study title | A randomised comparison between standard and flexible tip bougie (tracheal tube introducers) for tracheal intubation using non channelled videolaryngoscope | |
| Short study title | Standard vs flexible tip bougie for videolaryngoscopy | |
| Trial Design | Randomised control Trial | |
| Trial Participants | Patients aged 18 and above, presenting for elective surgical procedures where tracheal intubation is indicated | |
| Planned Sample Size | 160 | |
| Follow up duration | 3 to 24 hours | |
| Planned Trial Period | 18 months | |
| | Objectives | Outcome Measures |
| Primary | Ease of tracheal intubation | Modified Intubation Difficulty Scale Score |
| Secondary | Success rate at first attempt | Laryngoscopy time Intubation time Additional manoeuvres required Bougie impingement Bougie rotation Post op sore throat between 3 -24 hours post op Success of tracheal intubation |

Key Words: Intubation; tracheal, airway device; video laryngoscope

STUDY FLOW CHART

Figure 1: Flow of participants through the study

SCHEDULE OF OBSERVATIONS

Table 1: Schedule of Events

| Procedure | Screening | Baseline | Pre-Op | Intra-Op | Post-Op |
|--|-----------|----------|--------|----------|---------|
| Eligibility assessment | X | X | | | |
| Informed consent | | X | | | |
| Demographic data (DOB, sex, height and weight) | | X | | | |
| Details regarding operative procedure, Anaesthesia and method of airway management | | | X | | |
| Airway Assessment | | | X | | |
| Randomistaion | | | | X | |
| Laryngoscopy, Tracheal Intubation Laryngoscopy time, intubation time and modified intubation difficulty score | | | | X | |
| Post op visit- sore throat | | | | | X |

Contents

| | |
|---|----|
| SIGNATURE PAGE..... | 2 |
| Key Words: Intubation; tracheal, airway device; video laryngoscope..... | 4 |
| LIST OF ABBREVIATIONS | 9 |
| 1. INTRODUCTION | 10 |
| 2. RATIONALE | 12 |

1. INTRODUCTION

Videolaryngoscopes are devices which aid successful intubation of the trachea. Unlike standard (direct) laryngoscopes, they include a camera at the tip of the blade and display unit to provide an indirect view of the vocal cords (glottis). They are now routinely used for both standard and anticipated difficult tracheal intubation [1] and are recommended for difficult intubation in the national guidelines [2]. Some videolaryngoscopes have channel as a guide to help with the placement of a tracheal tube and some are without channel. The non-channelled videolaryngoscopes with acute-angled blades require a bougie or stylet to facilitate the passage of tracheal tube through the glottis into the trachea. One problem commonly encountered when using standard bougie is the tip of the bougie abutting on the anterior part of glottis and entrance to the windpipe (trachea) and not advancing further into the trachea [3]. This is known as anterior impingement. This can increase the likelihood of repeated intubation attempts, failed intubation and airway trauma. C-Mac is a commonly used non-channelled videolaryngoscope and has been shown to have high first attempt success rate as compared to other videolaryngoscopes [4, 5] and acute angled D-blade require a bougie to facilitate tracheal intubation [6].

The recently introduced flexible tip bougie likely to over comes the problem of anterior impingement due to the ability to flex the tip in the posterior direction once the tip enter the glottis. In a manikin study [7], the paramedics were able to intubate the trachea more efficiently using flexible tip bougie as compared to standard bougie. We are not aware of any study comparing these devices for success of tracheal intubation in patients. Comparing the efficacy of these devices could help inform

anaesthetists decisions in future when faced with a potentially difficult airway and has the potential to update current difficult airway guidelines.

1.1 Background

The recently introduced flexible tip bougie likely to overcome the problem of anterior impingement due to the ability to flex the tip in the posterior direction once the tip enter the glottis. In a manikin study [7], the paramedics were able to intubate the trachea more efficiently using flexible tip bougie as compared to standard bougie. We are not aware of any study comparing these devices for success of tracheal intubation in patients. Comparing the efficacy of these devices could help inform anaesthetists decisions in future when faced with a potentially difficult airway and has the potential to update current difficult airway guidelines.

1.2 Proposed study

We hypothesise that use of the flexible tip bougie will improve first attempt intubation success rates when compared to the standard bougie during laryngoscopy with non-channelled videolaryngoscopes. The intubation success rate is measured using modified intubation difficulty scale score (Appendix1). The score includes the points given to number of attempts at intubation, minor problems noticed during intubation such as bougie impingement, need for bougie rotation, need for tube rotation and percentage of glottic view obtained.

1.3 Study population

Patients aged above 18, presenting for elective surgical procedures and requiring tracheal intubation will be invited to take part in the study.

1.4 Treatment/ Intervention

On arrival to theatre, following standard WHO surgical safety check list, patients will be randomly allocated to have tracheal intubation either using standard bougie or a flexible tip bougie. The rest of the anaesthetic management will remain normal as planned by the lead anaesthetist. During tracheal intubation the data collected will included ease of tracheal intubation using modified intubation difficulty scale [8] and time taken to complete tracheal intubation.

1.5 Pre-clinical data

In a manikin study [7], the paramedics were able to intubate the trachea more efficiently using flexible tip bougie as compared to standard bougie.

1.6 Clinical Data

Both the standard and flexible tip bougies are used in clinical practice at University Hospitals Coventry and Warwickshire NHS Trust.

2. RATIONALE

2.1 Aims and hypothesis

We hypothesise that use of the flexible tip bougie will improve the intubation success rates when compared to the standard bougie during laryngoscopy with non-channelled videolaryngoscopes.

2.2 Justification

The DAS (Difficult Airway Society) guidelines, state that the best intubation effort is the first one. It emphasises on choosing appropriate devices for first attempt, these include laryngoscope and bougie along with optimum position. When using a non-channelled acute angled videolaryngoscope a bougie is essential to facilitate tracheal intubation. The standard bougie consists of a rigid material normally with an acute curve at the distal end (coude tip), which is rigid and fixed. Hence, anterior impingement is a common problem. The commonly used standard bougie is 14 French gauge Frova® airway intubation catheter (William Cook Europe, Bjaeverskov, Denmark). A flexible tip bougie (P3 medical Ltd, Bristol, UK) has a steerable blunt silicon tip and slider tabs which allows tip to be flexed anteriorly to facilitate the passage of the tip through the glottic opening, once advanced tip can be straightened or even retroflexed. Therefore, it can navigate around the curvature of a non-channelled videolaryngoscope more effectively. We are not aware of any study comparing this bougie with standard bougie for tracheal intubation when using videolaryngoscopes. A previous study looking at changing the head and neck position from traditional sniffing to neutral, didn't make any difference in the success

rate [3]. Comparing the efficacy of different bougies during videolaryngoscopy could inform airway practitioners on their choice of bougie in both normal and difficult airway scenarios when using such laryngoscopes.

2.3 Assessment and management of risk

For this study, patients requiring general anaesthesia and tracheal intubation for elective surgical procedures will be recruited. The videolaryngoscope (C-Mac non-channelled videolaryngoscope) and bougies selected for this study are used in routine clinical practice as intubation aids. In the event of any unanticipated difficulty with intubation, the lead anaesthetist will follow the Difficult Airway Society guidelines. The data collection will stop at this point.

The lead anaesthetist is free to choose a different airway equipment to those specified by the study, if they feel that this would be clinically appropriate. We do not anticipate any additional risks to the study participants. During the procedure of airway management, all patients will be closely monitored as specified by Association of Anaesthetists' standards of monitoring during anaesthesia. This includes peripheral oxygen saturation, end tidal oxygen, end-tidal CO₂, ECG and blood pressure.

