7.4 Blinding

Not Applicable. It will not be possible to blind the investigator the type of device used

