8. STATISTICS AND DATA ANALYSIS

8.1 Sample size calculation

From our previous study using CMAC videolaryngoscope and Frova bougie, mean mIDS was 1.75 and SD was 0.95 [5]. We considered a 30% reduction in mIDS to be clinically relevant. For standardized difference of 0.53, with a power of 0.9 and significance level of 0.05, we need 73 patients in each group. To account for failures and dropouts, we plan to recruit 160 patients in total.

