8.8 Procedure(s) to account for missing or spurious data

As the study duration is short, we unlikely to miss follow up of patients. All care would be taken to record all necessary data during preoperative visit and during

intubation. Very rarely the surgical plan may change, or surgery may be cancelled after recruiting. In total we need 146 patients to detect a significant difference in the modified intubation difficulty scale score. We have planned to recruit 160 in total to overcome any missing data or loss of follow up.

8.9 Other statistical considerations.

There is no plan to deviate from original statistics

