12.5 Safety reporting

We are not anticipating any adverse events as a result of study. However, any adverse events occurring during the study period will be reported as per the Trust policy using Datix.

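### Section 2.3 ends data collection at any unanticipated intubation difficulty, with no threshold or exemption, which conflicts with the unconditional sore throat visit and adverse-event reporting

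*Protocol*

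**What the plan says.** Section 2.3 (Assessment and management of risk) deals with intubation that turns out harder than foreseen. The lead anaesthetist follows the Difficult Airway Society guidelines, and "The data collection will stop at this point". The trigger is any such difficulty. No grade of difficulty is named, and nothing is said about which data the stop covers.

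Other parts of the protocol carry on without a condition:

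- The trial summary lists "Post op sore throat between 3 -24 hours post op" among the secondary outcome measures, and the schedule of events has a postoperative visit for it.
- Section 7.8 has patients reviewed at 3 to 24 hours as part of the standard postoperative visit.
- Section 12.5 says that "any adverse events occurring during the study period will be reported as per the Trust policy using Datix".

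Sore throat does not appear in the endpoint list in 3.4 or the assessment list in 7.7.

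Three further statements bear on who would be stopped. Section 7.4: "It will not be possible to blind the investigator the type of device used". Section 2.1 hypothesises that "use of the flexible tip bougie will improve the intubation success rates when compared to the standard bougie". Section 8.1: "To account for failures and dropouts, we plan to recruit 160 patients in total".

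**The concern.** The trigger occurs after randomisation and is closely related to outcome: in a trial about ease of intubation, recording ends when intubation becomes hard. If staff apply 2.3 literally, nobody records sore throat in those patients, and the comparison is made among the easier intubations only. Any difference between bougies that arises through difficult intubation would then be hidden. The Introduction itself describes that route. Of anterior impingement with a standard bougie it says: "This can increase the likelihood of repeated intubation attempts, failed intubation and airway trauma".

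The loss need not be equal in the two arms. The protocol's hypothesis implies more difficulty with the standard bougie, and the person who judges difficulty knows which bougie is in use. The first would remove more standard-bougie patients; the second could act in either direction. Sore throat not recorded within 24 hours cannot be recovered at analysis, and the extra recruitment in 8.1 replaces numbers but does not correct a selective loss.

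**Working it through.** **The conflict in the text.** In a stopped patient, 2.3 read literally allows no further data, while 7.8 and the schedule of events still require the sore throat visit and 12.5 still requires adverse-event reporting. No section says which prevails. Because 3.4 and 7.7 omit sore throat, a reader working from those lists would have no reason to treat it as protected.

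**The plan's own figures.** The protocol gives no rate of unanticipated difficulty and no rate of sore throat. The only related figure is the recruitment margin. Section 8.1 needs 73 per group, 2 × 73 = 146, and recruits 160, so the margin is 160 − 146 = 14 patients, or 14/160 = 8.75%. The 73 is close to reproducible: with a standardised difference of 0.53, 90% power and two-sided 5% (sidedness assumed), the normal approximation gives 75 per group; with the unrounded ratio 0.525/0.95 = 0.553 it gives 69. Nothing below depends on that gap.

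**How large the hidden difference could be.** Assume 80 per arm (160/2). Let kS and kF be the stopped patients in the standard and flexible arms, rE the sore throat risk in patients not stopped and rH the risk in stopped patients, each the same for both bougies. The full risk in an arm is rE + (k/80)(rH − rE). With stopped patients missing, both arms show rE and the observed difference is 0. The hidden difference is therefore

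(kS − kF)/80 × (rH − rE).

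Take 14 stopped patients as an illustration and rH − rE = 20 to 40 points (assumed):

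| Split kS/kF | (kS − kF)/80 | Hidden difference |
|---|---|---|
| 7/7 | 0 | 0 |
| 10/4 | 0.075 | 1.5 to 3.0 points |
| 14/0 | 0.175 | 3.5 to 7.0 points |

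A second illustration does not use the 14. Suppose 10% of standard and 5% of flexible patients are stopped (8 and 4 of 80), with risks of 50% in stopped and 20% in other patients. The hidden difference is 0.05 × 0.30 = 1.5 points. With 20% and 10% stopped (16 and 8 of 80) it is 0.10 × 0.30 = 3.0 points.

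**Compared with random error.** At an assumed overall risk of 22%, the standard error of the difference is √(2 × 0.22 × 0.78/80) = 0.065, about 6.5 points. All but the top of the 14/0 row lies below it.

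**What the data alone could not exclude.** With no assumption about rH, best-case and worst-case limits for the sore throat difference are (kS + kF)/80 apart. For 14 stopped patients that is 14/80 = 17.5 points, whatever the split; for 7 it is 7/80 = 8.75 points.

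**The case against.** The strongest reply is that 2.3 was never meant to reach so far. The stop follows directly on the switch to the rescue guideline, so it most naturally ends the intubation measurements. Ordinary difficulty stays inside the trial: section 7.3 prescribes rotating the bougie or the tube after a hold-up, and Appendix 1 scores extra attempts, extra operators and other manoeuvres, up to impossible intubation. A scale with those categories could not be completed if every difficulty ended recording. The postoperative visit and adverse-event reporting are nowhere cancelled. This stands in large part. It means that 2.3 contradicts other sections rather than clearly deleting data, and that perhaps few patients are affected. It does not remove the need to say so, because the sentence has neither threshold nor exemption and staff would have to interpret it during a difficult airway.

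Four stronger readings are tempting, and the documents do not support them:

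- *Airway-injury information is dropped.* Section 12.5 excludes no stopped patient, so injuries reported as adverse events would still reach Datix.
- *The stop causes the lack of a structured injury item.* No visible list contains one for any patient, so 2.3 is not the cause. The case report form is not shown.
- *The 14 spare patients are the stopped patients.* Section 8.1 mentions failures, which is consistent with that. But section 8.8, after stating "In total we need 146 patients to detect a significant difference in the modified intubation difficulty scale score", assigns the surplus to missing data and loss to follow-up, having just mentioned changed or cancelled surgery. The 14 is neither an estimate of stopped patients nor a ceiling on them.
- *The primary result is invalid.* A broad reading of the stop would also cut off mIDS in hard cases, but Appendix 1 shows that such cases are meant to be scored.

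**Conclusion.** The point holds as a conflict within the protocol. Section 2.3, read literally, removes a named secondary outcome after randomisation from the hardest intubations, and possibly unequally by bougie; 7.8, the schedule of events and 12.5 say otherwise.

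The size is unknown because the protocol gives no rates. Under the assumptions shown (80 per arm, the same sore throat risk for both bougies within stopped and within other patients, an excess of 20 to 40 points in stopped patients), the hidden difference is 0 to 3 points for plausible splits and at most 7 points if all 14 stopped patients were in one arm. That is probably modest against a standard error of about 6.5 points. It concerns one secondary outcome. It should be corrected because the contradiction is plain, the lost data cannot be recovered and the correction is cheap.

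**What to change.** In 2.3, replace the open-ended stop with wording such as: *The stop ends only the timed intubation measurements with the study device. The sore throat assessment at 3 to 24 hours and adverse-event recording, including any airway injury seen, continue for every randomised patient in whom laryngoscopy was attempted.* State that both are reported descriptively by allocated bougie. Add sore throat to 3.4 and 7.7 so that they match the trial summary.

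The cost is rewording in three sections and slight extra data entry for stopped patients. It uses the existing visit and the existing Datix route, with no extra patients and no change to the sample size.

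Optional, and separate from the fault in 2.3: one tick-box on the case report form for visible airway injury, completed for every patient, so that injury is asked about in the same way in both arms.

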3. OBJECTIVES AND OUTCOME MEASURES/ENDPOINTS

3.1 Primary objective

The aim of the study will be to see which of two bougies (an airway adjunct designed to pass through the vocal cords into the trachea in order to facilitate passage of a tracheal tube) is best suited for tracheal intubation (passage of a breathing tube into the trachea) when using a non-channelled videolaryngoscopes. The primary outcome will be ease of tracheal intubation, assed using modified intubation difficulty scale (mIDS) score (Appendix 1). The initial version of this scale was described and validated by Adnet et al [5].

3.2 Secondary objectives

Laryngoscopy time, time to successful tracheal intubation, overall first attempt success rate and visual analogue score for ease of use will be compared for two bougies.

3.3 Primary endpoint/outcome

The reported ease of intubation as measured using the modified intubation difficulty scale score.

3.4 Secondary endpoints/outcomes

- Time to successful tracheal intubation: It is time from when the videolaryngoscope is introduced into the oral cavity until the first capnography waveform is obtained.
- Laryngoscopy time: It is time from when the videolaryngoscope is introduced into the oral cavity to best view of the glottis (vocal cords)
- Overall first attempt success rate: This is the percentage of patients being successful at first attempt. This will be compared for two bougies.
- Anaesthetist's visual analogue score for ease of use of the bougie

4. STUDY DESIGN

Randomised Controlled trial

On arrival to theatre, following standard WHO surgical safety check list, patients will be randomly allocated to have tracheal intubation either using standard bougie or a flexible tip bougie.

5. STUDY SETTING

This will be a single centre study, conducted at University Hospitals Coventry & Warwickshire NHS Trust

6. ELIGIBILITY CRITERIA

Patients scheduled to undergo elective surgical procedures will be assessed for eligibility.

6.1 Inclusion criteria

Patients aged above 18, presenting for elective surgical procedures and requiring general anaesthesia tracheal intubation will be invited to take part in the study.

6.2 Exclusion criteria

- Patients who do not want to take part or do not give consent
- Patients below 18 years of age
- Patient physical status of ASA 4 and 5,
- Patients deemed to require awake intubation

7. TRIAL PROCEDURES

Suitable patients for the study will be screened from the operating theatre lists. During the preoperative period, one of the research team members will explain the study and provide a patient information sheet. Patients will be given adequate time to read the information and any questions will be answered. If they are satisfied and willing to take part in the study, written consent will be obtained.

7.1 Recruitment

The chief investigator and co-investigators will identify suitable operating lists on the and patients based on the scheduled surgical procedure. Only those patients meeting the inclusion criteria will be approached.

7.1.1 Patient identification

Patients undergoing surgery that requires tracheal intubation are suitable for inclusion in the study. Scheduled operating lists will be screened by the chief investigator and principle investigator and suitable patients will be identified.

During the preoperative assessment one of the research team member will provide a patient information sheet. Patients will be given adequate time to read the information and any questions will be answered. If they are satisfied and willing to take part in the study, written consent will be obtained.

7.1.2 Payment

There is no payment for any participant for taking part in the study

7.2 Consent

Participants will be given adequate time to read and understand the patient information leaflet. Once they have read the information, any questions will be answered. If they agree for the study, they will be asked to complete the consent form. The consent will be obtained by chief investigator, coinvestigator or one of the research team members, supervised by the investigators.

7.3 Randomisation scheme

Sample size: From our previous study using CMAC VL and Frova bougie, the standard deviation was 0.95 and mean mIDS was 1.75. We considered a 30% reduction in mIDS to be clinically relevant. For standardized difference of 0.53, with a power of 0.9 and significance level of 0.05, we need 73 patients in each group. To account for failures and dropouts, we decided to recruit 160 patients in total.

Randomisation for this study will be completed using sealed opaque envelopes. On arrival to the anaesthetic room, sealed envelope will be opened to reveal the group. Based on the group, following induction of general anaesthesia, the chosen bougie will be selected. It would be ensured that both type of bougies readily available in the airway trolley. Once the bougie is successfully placed in the trachea, tracheal intubation is completed as normal.

On arrival in the anaesthetic room, patients will be monitored using peripheral oxygen saturation, end-tidal CO₂, ECG and blood pressure. Both standard and flexible tip bougies will be kept ready for each study patient. Patient will be randomly allocated to one of two groups.

1. Flexible tip bougie
2. Standard bougie

All patients will be pre-oxygenated in a 15 to 20° head up position, to achieve a fractional ETO₂ of at least 0.8 prior to induction of anaesthesia. General anaesthesia will be induced at the discretion of lead anaesthetist. After the loss of consciousness was achieved, facemask ventilation will be commenced, and anaesthesia will be maintained with a volatile anaesthetic agent (age adjusted minimum alveolar concentration of 1.0) or using total intravenous technique as decided by the lead anaesthetist. Following the confirmation of the onset of neuromuscular blockade

using neuromuscular monitoring, in an optimal head and neck position, laryngoscopy will be performed using the videolaryngoscope as revealed by randomisation.

Following laryngoscopy, the chosen bougie will be passed through the glottis and advanced to the trachea. If there was any hold-up immediately after passing the bougie through the vocal cords, it will be gently rotated laterally so that the angle tip faced the lateral wall of trachea. Whilst railroading the tube, if there was any impingement at the level of arytenoids, the tube will be withdrawn slightly, rotated anti-clockwise and then advanced. The correct placement of the tube will be confirmed using end tidal CO₂. Rest of the anaesthetic management will proceed as planned by the lead anaesthetist.

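### Section 7.3 opens the randomisation envelope before induction without needing to, and section 7.4 gives no reason for leaving the patient and the sore-throat assessor unmasked

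*Protocol*

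**What the plan says.** Section 7.3 sets the moment of disclosure: "On arrival to the anaesthetic room, sealed envelope will be opened to reveal the group". It then gives the point at which the allocation is acted on: "Based on the group, following induction of general anaesthesia, the chosen bougie will be selected". It adds that "Both standard and flexible tip bougies will be kept ready for each study patient". After the steps up to confirmed neuromuscular block, it says "laryngoscopy will be performed using the videolaryngoscope as revealed by randomisation", and then "Following laryngoscopy, the chosen bougie will be passed through the glottis and advanced to the trachea".

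The whole of section 7.4 on blinding reads "Not Applicable. It will not be possible to blind the investigator the type of device used".

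The timing is not the same everywhere. Sections 1.4 and 4 allocate on arrival in theatre, after the safety checklist. The schedule of events (Table 1) puts randomisation in the intra-operative column. Section 8.7 describes the random choice as being made while the trachea is being intubated.

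Sore throat at 3 to 24 hours is listed as an outcome in the Trial Summary and as a postoperative item in Table 1. Section 7.8 describes the visit at which patients are reviewed in that window.

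**The concern.** The group is disclosed earlier than any step requires, at a time when the patient is likely to be awake in the room. Section 7.4 then treats blinding as one question with one answer, although its reason concerns only the person handling the device. The patient is anaesthetised when the bougie is used and has no need to know which one it was. The same may be true of the person who later asks about sore throat.

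Sore throat is reported by the patient. Someone who saw or heard that the newer or the standard device was to be used could answer differently, and an interviewer who knows the group could ask differently. The operator also knows the group while obtaining the glottic view. That knowledge may influence the POGO item (N4) of the primary score and laryngoscopy time, which is a secondary outcome.

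**Working it through.** The point turns on the order of events, so the passages are set side by side.

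1. **Order of steps in 7.3.** Arrival and envelope opening; monitoring; pre-oxygenation; induction; facemask ventilation; confirmed neuromuscular block; laryngoscopy; passage of the bougie. The envelope is opened at the first step. The bougie is selected after induction and first used at the last step.

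2. **Does any earlier step need the allocation?** Preparing the device does not, because both types are kept ready for every patient. Laryngoscopy does not either. The two groups listed in 7.3 are bougies, and section 2.3 names a single laryngoscope: "The videolaryngoscope (C-Mac non-channelled videolaryngoscope) and bougies selected for this study are used in routine clinical practice as intubation aids". The phrase in 7.3 that ties the videolaryngoscope to randomisation is therefore a slip and cannot justify early opening.

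3. **Who does the reason in 7.4 cover?**
   - *Operator, once the bougie is in use:* covered. Attempts, impingement, rotation, intubation time and the visual analogue score cannot be masked from this person.
   - *Patient:* not covered.
   - *Person asking about sore throat:* not covered. The protocol does not say who this is.

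4. **Which measures could be affected?**
   - *Sore throat:* patient-reported, so open to influence if the patient knows the group.
   - *Laryngoscopy time:* section 3.4 ends it at best glottic view, before the bougie is passed, with the group already known to the operator.
   - *POGO:* Appendix 1 scores N4 as 0 or 1. The protocol does not say when it is scored or by whom.

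5. **Can a size be given?** No. The documents report no sore-throat rate and no distribution for N4. Because N4 is 0 or 1, a net share *p* of one arm changing category moves that arm's mean score by *p* points, against a target difference of 0.30 × 1.75 = 0.525. Nothing in the documents supplies *p* or its direction, so the calculation stops there.

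**The case against.** Several objections have weight.

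- **The timing is not settled.** Table 1 and section 8.7 can be read as placing randomisation later than 7.3 does. This stands, and it is why the fix includes aligning the sections. Still, 7.3 is the operative instruction for the envelope, and sections 1.4 and 4 agree with it in substance.
- **Disclosure to the patient is inferred.** No passage says the patient is shown or told the group, and that the patient is awake follows only from the order of steps. The consent pages are not available. This stands: the protocol leaves the possibility open but does not show that it happens.
- **Sore throat has a light place in the plan.** It is absent from the outcome lists in 3.4 and 7.7. This limits the weight of the point without removing it.

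A reader might also infer more than the documents support.

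- *That allocation concealment is broken.* It is not. The envelopes are sealed and opaque, and Table 1 places consent and airway assessment before randomisation.
- *That any group difference in POGO or laryngoscopy time beyond chance must be bias.* Section 2.2 describes two devices that handle differently, so an operator may seek a different view for each. In an open device comparison that may be part of what is compared.
- *That a false-positive rate or a loss of power can be attached.* Both would rest on an invented shift in an assumed direction.
- *That the group should be withheld until best view is reached.* That would place device selection inside time to intubation, which section 3.4 starts when the laryngoscope enters the mouth. It would also change when the operator learns which device is to be used. It trades one problem for another and is not recommended.

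**Conclusion.** The point holds as a minor, low-cost improvement. Section 7.3 reveals the group earlier than its own sequence needs, the protocol places randomisation at different times in different sections, and the reason in 7.4 does not extend to the patient or the sore-throat assessor. The main exposure is a patient-reported secondary outcome; its size is unknown and probably small. An influence of the operator's knowledge on POGO and laryngoscopy time is possible but cannot be quantified, and later opening as proposed here does not remove it.

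This rests on two assumptions: that patients are awake when the envelope is opened, and that nothing outside the protocol already keeps the group from them or from the assessor. Section 7.4 is right about the operator.

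**What to change.** - **Section 7.3:** have a team member already present open the envelope after induction, out of the patient's awareness. This matches the point at which 7.3 already has the bougie selected. It leaves untouched the provision in 2.3 that "The lead anaesthetist is free to choose a different airway equipment to those specified by the study".
- **Timing:** use the same wording in Table 1 and in sections 1.4, 4, 7.3 and 8.7.
- **Section 7.4:** replace the present entry with a statement by role. The operator is not blinded. The patient and, where practicable, the person asking about sore throat are not told the group until that question has been answered.
- **Section 7.3, laryngoscopy sentence:** remove the words linking the videolaryngoscope to randomisation, since only the bougie is randomised.

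The cost is a few changes of wording and a slightly later envelope step, with no new staff or equipment.
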